7.4.1. Delays

In general, dose delays of 1 study drug (olaratumab, doxorubicin, or ifosfamide/mesna) due to toxicities outlined in [Section 7.4.3](#) will not necessitate delays of the other study drugs. However, close consideration must be made by the investigator to administer all study treatments per the schedule outlined in [Section 7.1](#).

Treatment may be delayed for up to 14 days to allow a patient sufficient time for recovery from study drug-related toxicity. If Day 8 treatment is delayed >7 days, treatment may be resumed with planned Day 1 treatment of the next cycle.

Dosing delay beyond 14 days may be permissible if AEs are not considered to be primarily related to olaratumab and the investigator deems continuation of study treatment to have clinical benefit for the patient. This decision has to be documented and be jointly made by the investigator and the Lilly team.

In the event of unforeseen circumstances or scheduling issues that require adjustments to the schedule, appropriate adjustments or delays to the schedule may be made following discussion between the investigator and the sponsor and written approval by the Lilly medical representative.

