10.3.2. Safety Analyses

All patients who receive at least 1 dose of any study therapy will be evaluated for safety and toxicity.

- Treatment-emergent adverse events will be summarized by MedDRA System Organ Class/preferred term, classified from verbatim terms. The incidence and percentage of patients with at least 1 occurrence of a preferred term will be included, according to the most severe NCI-CTCAE Version 4.0 grade. Causality (relationship to study drug), action taken, and outcome will be summarized separately. Duration of AE will be determined and included in the listings.
- Study drug exposure will be summarized for each arm with following variables: number of infusions, number of cycles, duration of therapy, cumulative dose, dose intensity, and relative dose intensity.
- Laboratory results will be classified according to NCI-CTCAE Version 4.0. Incidence of laboratory abnormalities will be summarized.
- Hospitalizations due to AEs, transfusions and vital signs will be summarized.

- DLTs will be summarized by phase in the patients who are evaluable for DLT assessments and listed by patient. ECG, ECHO/MUGA and immunogenicity data will also be summarized. Additional analyses may be performed as necessary. The details will be outlined in the SAP.

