5.8.1. Extent of Exposure

Drug exposure, dose intensity, drug adjustments (dose omissions, interruptions, reductions) and dose delays for olaratumab, doxorubicin, ifosfamide and mesna will be summarized for all treated patients.

Drug exposure will include the following summaries:

- Number of cycles received per patient
- Duration on therapy: $(\text{date of last cycle Day 1} - \text{date of first dose} + 21) \div 7$, [weeks]
- Cumulative dose: sum of dose administered at each infusion per patient per compound, [mg]
- Weekly dose intensity: the actual cumulative amount of drug taken divided by the duration of treatment in weeks
 - Olaratumab: cumulative dose / last available weight / duration of therapy, [mg/kg/week]
 - Doxorubicin: cumulative dose / BSA derived using last available weight / duration of therapy, [mg/m²/week]
 - Ifosfamide: cumulative dose / BSA derived using last available weight / duration of therapy, [mg/m²/week]
 - Mesna: cumulative dose / BSA derived using last available weight / duration of therapy, [mg/m²/week]
- Relative dose intensity: the actual amount of drug taken divided by the amount of drug prescribed times 100%, [%]

The summary of dose adjustments and delays will include the reason for adjustment or delays.

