5.8.3. Adverse Events

Adverse event (AE) severity grades will be assigned by the investigator using Common Terminology Criteria for Adverse Events (CTCAE) Version 4. AE verbatim text will be mapped by the sponsor or designee to corresponding terminology within MedDRA.

Pre-existing conditions are defined as any AEs that begin prior to the first dose of study drug.

Treatment-emergent adverse event (TEAE) are defined as any AE that occurred or worsened between the day of first dose and up to 30-day follow-up visit (or up to any time if serious and related to study treatment).

Comparisons of pre-existing conditions to on-treatment events at the low level term (LLT) level will be used in the treatment-emergent computation.

The following AE will be considered as **AE of special interest (AESI)** for the combination of olaratumab and doxorubicin, ifosfamide and mesna: infusion-related reactions (IRR), cardiac arrhythmias, cardiac dysfunction, encephalopathy, renal toxicity. PT for AESI are listed in [Appendix 1](#). Categories of AESI may be modified as the understanding of the safety of the investigational drug increases. The final list of categories will be reported in the clinical study report (CSR).

Consolidated AE will include Abdominal Pain, Anemia, Fatigue, Hyperbilirubinaemia, Hypertension, Hypoalbuminaemia, Hypokalaemia, Hypomagnesaemia, Hyponatraemia, Hypoproteinemia, Intestinal Obstruction, Leukocytosis, Leukopenia, Lymphopenia, Mucositis, Neuropathy, neutropenia, Musculoskeletal pain, Rash, and Thrombocytopenia. Each consolidated AE contains PTs identified as clinically identical or synonymous. PT for consolidated AEs are listed in [Appendix 2](#).

The following summaries and listings will be produced:

- Overview of AE
- Summary of TEAE by PT (any grade and Grade ≥ 3)
- Summary of DLT
- Summary of DET
- Summary of TEAE by system organ class (SOC) and PT (any grade and Grade ≥ 3)
- Summary of TEAE by SOC and PT and maximum grade (1-5)
- Summary of treatment-emergent serious AE (SAE) by SOC and PT (any grade and Grade ≥ 3)
- Summary of AEs as reason for study treatment discontinuation by SOC and PT
- Summary of and listing of TEAE leading to dose delays, omissions, interruptions, reductions, treatment discontinuation, hospitalizations, transfusions

- Summary of treatment-emergent AESI (any grade and Grade ≥ 3)
- Summary of treatment-emergent consolidated AE (any grade and Grade ≥ 3)
- Listings of DLT, DET, SAE, TEAE, AESI

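### SAP 5.8.1 defines relative dose intensity as a ratio of amounts with no time in it, so cycle delays cannot change it and dose reductions show only under one reading of the denominator

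*SAP*

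**What the plan says.** Protocol 10.3.2 lists the exposure variables to be summarised, ending with "dose intensity, and relative dose intensity", and defines neither. SAP 5.8.1 supplies the definitions. The first contains time: "Weekly dose intensity: the actual cumulative amount of drug taken divided by the duration of treatment in weeks". The next does not: "Relative dose intensity: the actual amount of drug taken divided by the amount of drug prescribed times 100" per cent. Duration on therapy is a single formula, the "date of last cycle Day 1" minus the date of first dose plus 21, divided by 7 to give weeks.

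The same section also commits to reporting modifications directly: "drug adjustments (dose omissions, interruptions, reductions) and dose delays for olaratumab, doxorubicin, ifosfamide and mesna will be summarized for all treated patients", and "The summary of dose adjustments and delays will include the reason for adjustment or delays". SAP 5.8.3 adds a "Summary of and listing of TEAE leading to dose delays, omissions, interruptions, reductions, treatment discontinuation, hospitalizations, transfusions". Protocol 10.3.3.5 plans summaries of omissions, reductions, delays and dose intensity by phase.

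On delays, Protocol 7.4.1 states: "Treatment may be delayed for up to 14 days to allow a patient sufficient time for recovery from study drug-related toxicity". It allows longer delays under stated conditions.

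**The concern.** In this SAP an intensity is an amount per week. A measure called relative dose intensity should then compare two weekly rates, but the stated formula compares two amounts. A patient who receives every dose in full, and late in every cycle, scores 100%.

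Delay is one of the protocol's built-in responses to marrow suppression. Protocol 7.4 sets neutrophil and platelet minimums for Day 1 dosing from Cycle 2 onward, and Table JGDR.11 delays the whole cycle when the neutrophil count is too low. Protocol 5.1 says that marrow suppression is relatively frequent with the backbone regimen. A reader of the study report who sees relative dose intensity near 100% would normally take it to mean that drug was delivered on schedule, which this number cannot show.

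The denominator is also open. *Prescribed* could mean the protocol starting dose or the dose ordered after a reduction, and the SAP does not say over which cycles it is summed. Two programmers could report different values from the same data.

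**Working it through.** The documents give no relative dose intensity figure to reproduce. The doxorubicin per-cycle total does reproduce: 25 × 3 = 75 mg/m².

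**Inputs**
- Cycle length 21 days, at most 6 combination cycles (Protocol 7.2.1).
- Doxorubicin 75 mg/m² per cycle (Protocol 5.1), so the planned rate is 75 / 3 = 25 mg/m²/week.
- Toxicity delay of up to 14 days (Protocol 7.4.1).
- Reduced doxorubicin doses of about 60 and then 45 mg/m² (Protocol 7.4.3.2.1, Table JGDR.11).
- Duration and intensity formulas from SAP 5.8.1.

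The delay and reduction patterns below are assumptions within the protocol's own limits. They are not predictions.

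**Formulas**, with a delay of d days before each of Cycles 2 to 6
- Weeks = (5 × (21 + d) + 21) / 7
- Weekly intensity = cumulative dose / weeks
- Time-based ratio = weekly intensity / 25
- SAP ratio = cumulative dose / amount prescribed

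For d = 14 at full dose: (5 × 35 + 21) / 7 = 28 weeks; 450 / 28 = 16.07; 16.07 / 25 = 64.3%. The SAP ratio is 450 / 450 = 100%.

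| Doses (mg/m²) | Delay (days) | Weeks | mg/m²/week | Time-based | SAP, starting dose | SAP, modified dose |
|---|---|---|---|---|---|---|
| 75 × 6 | 0 | 18 | 25.00 | 100% | 100% | 100% |
| 75 × 6 | 3 | 20.14 | 22.34 | 89.4% | 100% | 100% |
| 75 × 6 | 7 | 23 | 19.57 | 78.3% | 100% | 100% |
| 75 × 6 | 14 | 28 | 16.07 | 64.3% | 100% | 100% |
| 75, 60, 45 × 4 | 0 | 18 | 17.50 | 70.0% | 70% | 100% |
| 75, 60, 45 × 4 | 7 | 23 | 13.70 | 54.8% | 70% | 100% |
| 75, 60, 45 × 4 | 14 | 28 | 11.25 | 45.0% | 70% | 100% |

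The reduced course totals 75 + 60 + 180 = 315, and 315 / 450 = 70%. Delay moves neither SAP column. Reductions move one of them.

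Protocol 7.4.3.2.1 equates 75% of the starting dose with about 60 mg/m², but 0.75 × 75 = 56.25. Those figures need reconciling. The stated 60 is used here without judging which is right. With 56.25 the ratio would be 311.25 / 450 = 69.2%, so nothing turns on it.

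**Two properties of the weekly measure that a time-based ratio would inherit**
- *Duration is not stated per drug.* If olaratumab monotherapy cycles are counted, six undelayed full-dose doxorubicin cycles read 450 / 27 = 16.7 mg/m²/week after three monotherapy cycles, or 450 / 36 = 12.5 after six, instead of 25.
- *The amount is divided by the last available weight, or by body surface area derived from it.* Protocol 7.2.1 does not require recalculation while weight stays within 10%. If the olaratumab dose in mg is unchanged and weight has fallen by nearly 10% at the end, the result is inflated by up to about 1 / 0.9 = 1.11.

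**The case against.** The strongest reply is that the SAP does not lose the information. Weekly dose intensity falls when cycles are late. Duration and cycle count together show six cycles taking 28 weeks. Delays and reductions are summarised with reasons for all four drugs, and the adverse events behind them are summarised and listed. This stands. A reader might infer that the SAP conceals delays, and the documents do not support that. One qualification applies: the weekly figure for the chemotherapy drugs may be diluted by monotherapy time, though the delay summary does not depend on it.

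A reader might also infer that a flattering value could steer dose selection. Table JGDR.7 decides on counts of patients with Cycle 1 DLTs. Later safety data may be considered, but no rule, threshold or sample-size calculation uses relative dose intensity. Nor is preserving delivery of the backbone a stated objective. The primary objective is the safety profile and a regimen for a future Phase 2 study.

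The 14-day row is an extreme. Under Table JGDR.11, neutropenic fever or infection, or prolonged Grade 4 neutropenia, leads to dose reduction and, at a third incidence, to stopping the combination. Full doses with the maximum delay every time would not arise from those events if the guidelines were followed. Slow count recovery without them could still delay full-dose cycles.

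Finally, it is tempting to say that reductions are hidden as well. That is true only if *prescribed* means the modified dose. The text does not settle it, so this part is an ambiguity and not an error.

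These replies limit the consequence. None of them lets a delay enter the ratio.

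**Conclusion.** The formula is wrong for the quantity it names. Under either reading of the denominator, delay has no effect on the SAP's relative dose intensity. In the assumed full-dose doxorubicin courses it stays at 100% while the time-based value is 89.4%, 78.3% or 64.3% for 3-, 7- or 14-day delays. For the assumed reduced-dose course without delay, it is 70% or 100% depending on an undefined word.

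The consequence is limited to one descriptive exposure line that can mislead and that sits beside other outputs showing the delays and reductions. The sizes depend on the assumed patterns. That delay cannot enter the ratio follows from the formula alone. It should be corrected in the SAP, but it does not threaten the trial's design or its dose decisions.

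**What to change.** In SAP 5.8.1, define relative dose intensity = 100 × actual weekly dose intensity / planned weekly dose intensity, and specify:

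- **Duration per drug.** Exclude olaratumab monotherapy cycles for doxorubicin, ifosfamide and mesna.
- **Denominator.** Use the assigned cohort's protocol starting dose over the cycles started. In the loading-dose cohort this includes the Cycle 1 amount: over six cycles, (40 + 5 × 30) / 18 = 10.56 mg/kg/week against 180 / 18 = 10 without loading. In a reduced-ifosfamide cohort it is 7.5 / 3 = 2.5 g/m²/week against 10 / 3 = 3.33. For mesna the protocol gives only a minimum, so the SAP must say what is taken as planned.
- **Numerator.** Normalise each cycle's amount by the weight or body surface area used for dosing in that cycle, so that later weight change does not distort the ratio.

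If the present ratio is kept, rename it percent of planned dose and define the denominator as the protocol starting dose.

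The cost is SAP wording and a little more programming. The reported figures may look less favourable where delays are common. Patient management does not change.

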5.8.2. Dose-Limiting Toxicity and DLT-Equivalent Toxicities

The definition and derivation of the dose limiting toxicities (DLT) and the DLT-equivalent toxicities (DET) is specified in Protocol JGDR, Section 7.2.2.

DLT will be summarized and listed for DLT-evaluable population. DET will also be listed and summarized for safety population.

5.8.3. Adverse Events

Adverse event (AE) severity grades will be assigned by the investigator using Common Terminology Criteria for Adverse Events (CTCAE) Version 4. AE verbatim text will be mapped by the sponsor or designee to corresponding terminology within MedDRA.

Pre-existing conditions are defined as any AEs that begin prior to the first dose of study drug.

Treatment-emergent adverse event (TEAE) are defined as any AE that occurred or worsened between the day of first dose and up to 30-day follow-up visit (or up to any time if serious and related to study treatment).

Comparisons of pre-existing conditions to on-treatment events at the low level term (LLT) level will be used in the treatment-emergent computation.

The following AE will be considered as **AE of special interest (AESI)** for the combination of olaratumab and doxorubicin, ifosfamide and mesna: infusion-related reactions (IRR), cardiac arrhythmias, cardiac dysfunction, encephalopathy, renal toxicity. PT for AESI are listed in [Appendix 1](#). Categories of AESI may be modified as the understanding of the safety of the investigational drug increases. The final list of categories will be reported in the clinical study report (CSR).

Consolidated AE will include Abdominal Pain, Anemia, Fatigue, Hyperbilirubinaemia, Hypertension, Hypoalbuminaemia, Hypokalaemia, Hypomagnesaemia, Hyponatraemia, Hypoproteinemia, Intestinal Obstruction, Leukocytosis, Leukopenia, Lymphopenia, Mucositis, Neuropathy, neutropenia, Musculoskeletal pain, Rash, and Thrombocytopenia. Each consolidated AE contains PTs identified as clinically identical or synonymous. PT for consolidated AEs are listed in [Appendix 2](#).

The following summaries and listings will be produced:

- Overview of AE
- Summary of TEAE by PT (any grade and Grade ≥ 3)
- Summary of DLT
- Summary of DET
- Summary of TEAE by system organ class (SOC) and PT (any grade and Grade ≥ 3)
- Summary of TEAE by SOC and PT and maximum grade (1-5)
- Summary of treatment-emergent serious AE (SAE) by SOC and PT (any grade and Grade ≥ 3)
- Summary of AEs as reason for study treatment discontinuation by SOC and PT
- Summary of and listing of TEAE leading to dose delays, omissions, interruptions, reductions, treatment discontinuation, hospitalizations, transfusions

- Summary of treatment-emergent AESI (any grade and Grade ≥ 3)
- Summary of treatment-emergent consolidated AE (any grade and Grade ≥ 3)
- Listings of DLT, DET, SAE, TEAE, AESI

The TEAE and SAE summaries will be produced for all TEAE/SAEs and repeated for TEAE/SAE related to study treatment, where relationship of the AE to the study treatment will be assessed by the investigator (yes or no).

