Radiologic imaging and measurement of palpable or visible lesions	X	X*	
*For patients whose disease has not progressed: Perform q 6 weeks × 2, then q 3 mo until:
 
 the patient has objective disease progression according to RECIST 1.1 or the study's primary/final analysis 
Perform using the same method used at baseline and throughout the study.
 
For patients who have had objective disease progression: Radiologic tests and measurement of palpable or visible lesions are no longer required; these patients should be followed up for OS and collection of post-study treatment anticancer therapy information collection as indicated below.

Collection of survival information		X	Perform q 2 mo (±7 days) for the first 2 years after discontinuation from study treatment and q 6 mo (±14 days) thereafter until death or study completion. If an in-person visit is not possible, confirm survival by contacting the patient directly via phone.
Collection of post-study treatment anticancer therapy information	X	X	Perform q 2 mo (±7 days) for the first 2 years after discontinuation from study treatment and q 6 mo (±14 days) thereafter until death or study completion.
ECG	X	X	
 All patients should have a 12-lead ECG performed at short-term follow-up. Patients should also have a 12-lead ECG performed approximately 6 months (±7 days) and 12 months (±7 days) after the end of treatment with doxorubicin and ifosfamide.

Procedure	Short-Term Follow-Up ^a	Long-Term Follow-Up	Instructions
Visit	801	802-8XX	
Echocardiogram and/or MUGA scan		X	Perform at 6 months (± 7 days) and 12 months (± 7 days) after the end of treatment with doxorubicin and ifosfamide. Echocardiograms/MUGA scans may be discontinued if the patient begins another anticancer therapy. Perform additional evaluations in the setting of cardiac symptoms and/or at the discretion of the investigator.
Hematology	X		See Appendix 3 . To be performed locally for patient management and centrally for analysis purposes.
Coagulation	X		See Appendix 3 . To be performed locally.
Clinical chemistry	X		See Appendix 3 . To be performed locally for patient management and centrally for analysis purposes.
Urinalysis	X		See Appendix 3 . To be performed locally.
Sample collection			For all sample collection, see Appendix 4 .
Pharmacodynamics			
Pharmacokinetics			
Immunogenicity			
Pharmacogenetics			
Other biomarkers			

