3.2.1. Rationale for Amendment (a)

The original Study JGDR protocol, version dated 14 March 2017, was amended to remove visits and/or procedures not intended for patients receiving olaratumab monotherapy only after completing 6 cycles of olaratumab plus doxorubicin and ifosfamide (or discontinued doxorubicin and ifosfamide before). In particular, visits and procedures specifically used to administer and monitor for toxicity from the doxorubicin and ifosfamide combination have been removed for patients receiving olaratumab monotherapy.

The timing of ECHO/MUGA scans after discontinuation of doxorubicin plus ifosfamide treatment was clarified and ECG evaluations were added at the same frequency to ensure complete evaluation of any potential cardiotoxic effects following treatment with doxorubicin plus ifosfamide.

The wording pertaining to required contraceptive use following study treatment has been clarified to align with label requirement for doxorubicin.

In addition, some minor editorial changes have been made throughout the protocol to improve clarity and practicality of the protocol and secure alignment with the intended study design.

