9.2.1. Serious Adverse Events

An SAE is any AE from this study that results in 1 of the following outcomes:

- death
- initial or prolonged inpatient hospitalization
- a life-threatening experience (that is, immediate risk of dying)
- persistent or significant disability/incapacity
- congenital anomaly/birth defect
- considered significant by the investigator for any other reason: important medical events that may not result in death, be life-threatening, or require hospitalization; may be considered serious, based upon appropriate medical judgment.

Although all AEs after signing the ICF are recorded in the eCRF, SAE reporting begins after the patient has signed the ICF and has received study treatment. However, if an SAE occurs after signing the ICF, but prior to receiving study treatment, it needs to be reported ONLY if it is considered reasonably possibly related to study procedure.

Study site personnel must notify Lilly or its designee of any SAE within 24 hours of investigator awareness of the event via a Lilly-approved method. If alerts are issued via telephone, they are to be immediately followed with official notification on study-specific SAE forms. This 24-hour notification requirement refers to the initial SAE information and all follow-up SAE information.

Pregnancy (during maternal or paternal exposure to study treatment) does not meet the definition of an AE but should be reported. However, to fulfill regulatory requirements, any pregnancy should be reported following the SAE process to collect data on the outcome for both mother and fetus.

All AEs and SAEs, regardless of relatedness to study drugs or protocol procedures, occurring during the safety follow-up visit (Visit 801; approximately 30 days after completion of study therapy) must be reported to Lilly or its designee. Investigators are not obligated to actively seek AEs or SAEs in patients beyond Visit 801. However, if the investigator learns of any SAE, including a death, at any time after a patient has been discharged from the study, and he/she considers the event reasonably possibly related to the study treatment or study participation, the investigator must promptly notify Lilly.

Planned hospitalizations or procedures for preexisting conditions that were recorded in the patient's medical history at the time of enrollment should not be considered SAEs.

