9.4. Safety

9.4.1. Other Safety Measures

For each patient, ECGs, vital signs, laboratory tests, or other tests should be collected as shown in the Schedule of Activities (Section 2).

Any clinically significant findings that result in a diagnosis and that occur after the patient receives the first dose of study treatment should be reported to Lilly or its designee as an AE via eCRF.

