5.8.8. Electrocardiograms, Echocardiogram / Multiple Gated Acquisition Scan

Electrocardiograms (ECG) findings that are considered to be a medical history condition or an AE will be summarized and listed.

Left ventricular ejection fraction (LVEF) results will be summarized by scheduled time point.

Changes in LVEF will also be summarized including percentage of patients with LVEF decrease of $\geq 10\%$ and below the lower limit of normal, or an absolute decrease of 20%, or an absolute LVEF decreases to or below 40%.

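### For patients off treatment, cardiac events first found at the 6- and 12-month post-doxorubicin tests stay out of the AESI summary unless serious and related, and AE recording is not scheduled there

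*SAP*

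**What the plan says.** **Counting window.** SAP 5.8.3 defines a treatment-emergent event as "any AE that occurred or worsened between the day of first dose and up to 30-day follow-up visit", extended only by the clause "or up to any time if serious and related to study treatment". The AESI table is a "Summary of treatment-emergent AESI". Cardiac arrhythmias and cardiac dysfunction are named AESIs in Protocol 9.2.3 and SAP 5.8.3. SAP Appendix 1 includes terms that a test alone can produce, such as a fall in ejection fraction or a prolonged QT interval.

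**Late tests.** Table JGDR.3 places ECG and ECHO/MUGA in long-term follow-up: "Patients should also have a 12-lead ECG performed approximately 6 months" and again at 12 months after doxorubicin and ifosfamide end. ECHO/MUGA follows the same timing. Table JGDR.2 schedules the same tests for patients on olaratumab monotherapy, with continuous AE collection. Protocol 3.2.1 explains that ECGs were added "to ensure complete evaluation of any potential cardiotoxic effects following treatment with doxorubicin plus ifosfamide".

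**AE recording.** Table JGDR.3 marks AE collection at Visit 801 and not in long-term follow-up. Protocol 9.2.1 states: "Investigators are not obligated to actively seek AEs or SAEs in patients beyond Visit 801". Protocol 9.4.1 sets no end date: "Any clinically significant findings that result in a diagnosis and that occur after the patient receives the first dose of study treatment should be reported" as an AE.

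**Test summaries.** SAP 5.8.8 says of ECGs that "findings that are considered to be a medical history condition or an AE will be summarized and listed". LVEF is summarized at each scheduled time point, with the percentage of patients crossing set decrease thresholds.

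**The concern.** The window closes on one clock and the late cardiac tests run on another. Visit 801 is timed from the decision to stop all study treatment, the tests from the end of doxorubicin and ifosfamide. Two patients with the same non-serious arrhythmia at the same time after doxorubicin are therefore treated differently if one has stopped olaratumab and the other has not. Only the second contributes to the AESI rate.

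At stake is whether the AESI summary reflects what these tests were scheduled to find. ECG findings are the more exposed, because they reach an output only through a medical-history or AE record, and the follow-up schedule does not provide for AE recording at these visits. The cardiac-toxicity subgroup by dexrazoxane use in SAP 5.10 would inherit the same cut-off if it is built on treatment-emergent AESIs.

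**Working it through.** The plan states no figure on this point, so the check is date arithmetic followed by tracing each kind of finding to its output.

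**Inputs.** Cycles of 21 days, at most six (Protocol 7.2.1). Last ifosfamide on Day 4, or Day 3 at the reduced dose (Table JGDR.6). Visit 801 at 30 ± 7 days from the stop decision (Table JGDR.3, footnote a). Late tests at ±7 days off treatment (Table JGDR.3) or ±14 days on monotherapy (Table JGDR.2). Month = 365/12 days (SAP 5.2.2). Assumptions: the late-test clock starts at the last ifosfamide dose; the stop decision falls between Days 8 and 21 of Cycle 6, with 14 days later as an outer case.

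**1. When the window closes.** Cycle 6 Day 1 is study day 5 × 21 + 1 = 106, so the last ifosfamide dose is on day 109 (full) or 108 (reduced). The stop decision falls on days 113 to 126, outer case 140.
- Earliest Visit 801: 113 + 30 − 7 = 136, which is 136 − 109 = 27 days after chemotherapy.
- Latest: 126 + 30 + 7 = 163, which is 163 − 108 = 55 days after.
- Outer case: 140 + 37 = 177, which is 177 − 108 = 69 days after.

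**2. When the tests come.** Six months is 6 × 365/12 = 182.5 days, earliest 175.5. Twelve months is 365 days, earliest 358. The smallest gaps after the window closes are 175.5 − 69 = 106.5 days and 358 − 69 = 289 days. Starting the late-test clock at the end of the cycle would widen both.

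**3. How long olaratumab must continue for the test to count.** For the 6-month test: 182.5 − 30 = 152.5 days after chemotherapy. Over the visit windows the range is 182.5 − 14 − 37 = 131.5 to 182.5 + 14 − 23 = 173.5 days, or about 6 to 8 cycles. For the 12-month test: 365 − 30 = 335 days, range 314 to 356, or about 15 to 17 cycles.

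**4. Where a finding at a late test goes.**

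| Finding | Off treatment, after Visit 801 | Still on olaratumab |
|---|---|---|
| Non-serious, recorded as an AE | Not in the AESI summary; can reach the AESI listing and, if from ECG, the 5.8.8 summary | AESI summary |
| ECG finding not recorded as an AE or medical history | No planned output | No planned output, but AE collection is continuous |
| Serious, judged unrelated | Not in the AESI summary; registry dataset (SAP 5.14) if recorded | AESI summary |
| Serious and related | AESI summary | AESI summary |
| LVEF value | LVEF summary | LVEF summary |

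**5. Who reaches the tests.** Protocol 5.3 completes the study 30 days after all Dose Confirmation patients end combination therapy. Protocol 7.9.1 ends long-term follow-up when continued access begins, and Table JGDR.4 schedules no ECG or ECHO/MUGA. Ignoring visit windows, a patient reaches the 6-month test before completion only if their own chemotherapy ended at least 182.5 − 30 = 152.5 days (about 5 months) before the last Dose Confirmation patient's combination therapy. For the 12-month test the lead must be 365 − 30 = 335 days (about 11 months). Fifteen of the 30 patients planned on the recommended regimen come from the Dose Confirmation Phase, so many of them may never have these tests.

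**The case against.** A treatment-emergent rate that closes at a 30-day visit is a defined measure and omits later events by design. Much of the late cardiac information also has another route. LVEF falls appear in the LVEF summary whatever the window. ECG findings recorded as AEs are summarized under SAP 5.8.8 without a treatment-emergent restriction, and the AESI listing in SAP 5.8.3 is not worded as treatment-emergent. Events that are serious and related count at any time. Having no duty to seek AEs actively does not forbid recording them, and Protocol 9.4.1 still asks for diagnoses to be reported. Patients off treatment will often have progressed, and ECHO/MUGA may stop once another anticancer therapy starts. Dose decisions rest mainly on Cycle 1 DLTs.

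All of this stands and narrows the point. A reader might infer that late LVEF decreases are lost or that late ECG findings can appear nowhere; the first is wrong, and the second is true only of findings that nobody records. None of it, however, puts a non-serious late event into the AESI rate table or schedules AE recording at the visits where the tests are done. Protocol 9.2.1 and 9.4.1 can be read together, but sites are left to work out how.

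**Conclusion.** The point holds for patients off all study treatment who reach the 6- or 12-month tests before study completion or the end of long-term follow-up. For them, a cardiac event first found at these tests is outside the AESI summary unless it is both serious and related, while the same finding on olaratumab monotherapy is counted. The loss has two parts: late ECG findings not recorded as AEs, and late cardiac events missing from the AESI rate table.

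The timing does not depend on fine assumptions, since the smallest gap is about 106 days even with a late stop decision. The number of patients affected cannot be derived: the documents give no accrual pattern, no distribution of monotherapy duration and no rate of late cardiac findings. A reader might infer that the AESI rate is understated by some percentage, or that cohorts are biased differently because their treatment durations differ. The documents support neither, as any percentage would rest on invented inputs and no cohort durations are given. This is a worthwhile, inexpensive improvement to safety reporting and does not call the dose-finding decisions into question.

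**What to change.** 1. In SAP 5.8.3, keep the treatment-emergent window and add a separate row for cardiac arrhythmia and cardiac dysfunction AESIs with onset after Visit 801, regardless of seriousness or relatedness. Flag onset after new anticancer therapy, and use as denominator the patients who had the late assessment.
2. In Table JGDR.3 and Protocol 9.2.1, state that clinically significant findings from the scheduled late ECG and ECHO/MUGA are recorded as AEs, in line with 9.4.1.
3. In SAP 5.8.8, list ECG results at the 6- and 12-month time points.
4. State beside these outputs that the assessments exist only for patients who reach them before study completion or the end of long-term follow-up.

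The cost is a few lines in the SAP, a schedule entry and a sentence in the protocol, and the AE form kept open at visits already planned. No test is added. The downside is slightly more AE recording, and some late events will be confounded by later therapy; the flag makes these visible but cannot remove the confounding.
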